2.5 Scientific Steering Committee

The Scientific Steering Committee (SSC) will closely review the safety data throughout the study to evaluate the risk/benefit ratio in general and for the separate prospective subgroups following a predefined Safety Management Plan

3 OBJECTIVES

3.1 Primary

The primary objective of this study is:

- To determine the incidence of high-grade (CTCAE v4.0 Grade 3 or higher), treatment-related, select adverse events in subjects with histologically confirmed stage III (unresectable) or stage IV melanoma and progression after prior treatment containing an anti-CTLA-4 monoclonal antibody treated.

3.2 Secondary

The secondary objectives of this study are:

- To determine the incidence and to characterize the outcome of all high-grade (CTCAE v4.0 Grade 3 or higher), select adverse events in subjects with histologically confirmed stage III (unresectable) or stage IV melanoma and progression after prior treatment containing an anti-CTLA-4 antibody;
- To estimate OS in all treated subjects.

4 ENDPOINTS

4.1 Primary Endpoint

The primary endpoint is the incidence for high-grade (CTCAE v4.0 Grade 3 or higher), treatment-related, select adverse events. The select Adverse Events consist of a list of preferred terms grouped by specific category as follows:

- Pulmonary toxicity
- Gastrointestinal toxicity (diarrhea or colitis)
- Endocrinopathies
- Hepatotoxicity (including asymptomatic LFT elevations)
- Renal toxicity
- Skin toxicity
- Hypersensitivity/Infusion site reaction

4.2 Secondary Endpoints

The secondary endpoints include the incidence of all high-grade (Grades 3 and higher) select adverse events, the median time to onset and median time to resolution (Grades 3-4) of select adverse events, the and overall survival (OS) of subjects.

4.2.1 Incidence of all High-grade, Select AEs

The incidence for high-grade (CTCAE v4.0 Grade 3 or higher), select adverse events. The select Adverse Events consist of a list of preferred terms grouped by specific category as follows:

- Pulmonary toxicity
- Gastrointestinal toxicity (diarrhea or colitis)
- Endocrinopathies
- Hepatotoxicity (including asymptomatic LFT elevations)
- Renal toxicity
- Skin toxicity
- Hypersensitivity/Infusion site reaction

[Redacted]

- [Redacted]
- [Redacted]
- [Redacted]
- [Redacted]
- [Redacted]

[Redacted]

- [Redacted]

[Redacted]

- [Redacted]
- [Redacted]
- [Redacted]
- [Redacted]
- [Redacted]
- [Redacted]
- [Redacted]
- [Redacted]
- [Redacted]

[Redacted]

[Redacted]

Table 3: Time Windows for Assessments

Nominal Time-Point	Time Window
Week 1 (Baseline)	Prior to first dose on Day 1
Week 5	Day 2 thru Day 55, inclusive
Every 4 weeks up to Week 13	Nominal day (+26 days/-2 days, inclusive)
Week 17	Nominal day 113 (+54 days/-2 days, inclusive)
Every 8 weeks thereafter	Nominal day (+54 days/-2 days, inclusive)
Follow-up 1 (EQ-5D-3L only)	If assessment is post last dose and within 30 days of last dose (+68-82 days/-2 days, inclusive)
Follow-up 2 (EQ-5D-3L only)	If assessment is post 70-84 days of Follow-up 1 (+89 days/-2 days, inclusive)
Every 3 months thereafter (EQ-5D-3L only)	If assessment is after Follow-up 1 and Follow-up 2 (+89 days/-2 days, inclusive)

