- b Serum chemistry tests include blood urea nitrogen [BUN] or serum urea level, serum creatinine, sodium, calcium, chloride, lipase, and glucose. Amylase should be performed in addition to lipase in cases where lipase results are not available prior to dosing.
- c Liver function tests include AST, ALT, total bilirubin, alkaline phosphatase, albumin.
- d Thyroid function testing including TSH (free T3 and free T4 if abnormal results for TSH).

Table 5.1-3: Off-Treatment Follow-Up Assessments:CA209172

Procedure	Every 4 Weeks	FU-X01 (30 days ±7 days)	FU-X02 (70-84 days after FU- X01 ±7 days)	Follow-Up After X01 and X02. Every 3 months. (±7 days)	Notes
Safety Assessments					
Physical Examinations		X	X		Collect weight and ECOG PS. Focused physical examination may be performed if clinically indicated.
Vital Signs and Oxygen Saturation		X	X		Temperature, BP, HR, RR, O2 saturation by pulse oximetry at rest (also monitor amount of supplemental oxygen if applicable) prior to dosing and at any time a patient has any new or worsening respiratory symptoms.
Adverse Events Assessments		X	X		Beyond 100 days from the last dose of study therapy, patients followed for ongoing drug-related adverse events until resolved, symptoms return to baseline or are deemed irreversible, lost to follow-up, or withdrawal of study consent.
		■	■		
Laboratory Tests		X	X		Serum chemistry tests and TFTs should be checked at FU1 and FU2.
Pregnancy Test	X	X	X		Pregnancy testing may be performed at home if an in-office visit is otherwise not required.
Efficacy Assessments					
Tumor Scans				-----see notes-----	Tumor progression scans are recommended to be completed as required by local standards of care or at the investigator's discretion.

Table 5.1-3: Off-Treatment Follow-Up Assessments:CA209172

Procedure	Every 4 Weeks	FU-X01 (30 days ±7 days)	FU-X02 (70-84 days after FU- X01 ±7 days)	Follow-Up After X01 and X02. Every 3 months. (±7 days)	Notes
Survival Follow-up		X	X	X ^a	
Outcomes Assessments					
EQ-5D-3L		X	X	X ^a	The EQ-5D-3L can be completed by mail, e-mail, or telephone call (using the telephone version) when a clinical visit is not otherwise required. When a clinical visit is required, the questionnaire should be completed at the clinic.

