4.3.3.2 EuroQoL EQ-5D-3L

Subjects' reports of general health status will be assessed using the EuroQoL Group's EQ-5D-3L. EQ-5D-3L essentially has 2 components: the descriptive system and the visual analogue scale (VAS).

The instrument's descriptive system consists of 5 dimensions: mobility, self-care, usual activities, pain/discomfort, and anxiety/depression. Each dimension has 3 levels, reflecting "no health problems," "moderate health problems," and "extreme health problems." A dimension for which there are no problems is said to be at level 1, while a dimension for which there are extreme problems is said to be at level 3. Thus, the vectors 11111 and 33333 represent the best health state and the worst health state, respectively, described by the EQ-5D-3L. Altogether, the instrument describes $3^5 = 243$ health states. Empirically derived weights can be applied to an individual's responses to the EQ-5D-3L descriptive system to generate an index measuring the value to society of his or her current health. Such preference-weighting systems have been developed for the UK, US, Spain, Germany, and numerous other populations. For this study, EQ-5D-3L utility index values will be computed using a scoring algorithm based on the United Kingdom Time-Trade-Off (UK TTO) value set²

In addition, the EQ-5D-3L includes a VAS, which allows respondents to rate their own current health on a 101-point scale ranging from 0="worst imaginable" health to 100="best imaginable" health state³.

A change from baseline of 0.08 for the EQ-5D-3L utility index score and of 7 for the EQ-5D-3L VAS are considered minimally important differences for the EQ-5D-3L⁴.

All questionnaires completed at baseline and on-study will be assigned to a time-point according to the windowing criteria in Table 3 and included in the analysis. In case a subject has two on-study assessments within the same window, the assessment closest to the time-point will be used.

And, in the case of two assessments at a similar distance to the time-point, the latest one will be chosen. In the event where the subject has no assessment at all in a specific window, the observation will be treated as missing for that time-point.

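### SAP Table 3: each adjacent pair of post-baseline on-treatment QoL windows shares one day, and the EQ-5D-3L follow-up windows do not match the protocol's ±7-day visits

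*SAP*

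**What the plan says.** SAP Table 3 (Time Windows for Assessments) sets the post-baseline windows. The first of them, for the Week 5 visit, is stated in fixed study days as "Day 2 thru Day 55, inclusive". For the Week 9 and Week 13 visits the table instead sets limits around the planned day, written "Nominal day (+26 days/-2 days, inclusive". From Week 17, which it places at Day 113, visits come 8 weeks apart and the upper limit widens to +54, with the lower limit still at -2 and both ends counted.

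Three further rows concern the EQ-5D-3L alone. The row for the first follow-up visit reads "If assessment is post last dose and within 30 days of last dose (+68-82 days/-2 days, inclusive". The second visit is placed by a range, 70 to 84 days from the first, and carries limits of +89 and -2. The 3-monthly contacts carry the same two limits.

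SAP Section 4.3.3.2 gives the assignment rules. "In case a subject has two on-study assessments within the same window, the assessment closest to the time-point will be used"; if two forms are equally close, the later one is taken. A time-point whose window holds no form is treated as missing.

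Protocol Table 5.1-2 allows ±2 days for on-treatment visits. Protocol Table 5.1-3 allows 7 days either side at all follow-up contacts: the first visit is headed "FU-X01 (30 days ±7 days", and the same tolerance applies to the second visit and to the 3-monthly contacts.

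**The concern.** Windows meant to divide follow-up time should place each form in exactly one time-point. In Table 3 the upper limit of each post-baseline on-treatment window is the same day as the lower limit of the next, and both limits are inclusive. The rules in Section 4.3.3.2 deal with two forms in one window and with an empty window. They do not deal with one form in two windows.

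In follow-up, the early side of the SAP windows is 5 days narrower than the visit tolerance in the protocol. A form collected on a permitted day can therefore be assigned to the wrong time-point, and its own time-point is then recorded as missing.

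At stake are the by-visit mean scores, the mean changes from baseline and the completion rates in SAP Sections 7.8.1 and 7.8.2. Two programmers following the same text could produce different figures.

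**Working it through.** **Reproducing the plan's own figures.** Take nominal day = 7 × (week − 1) + 1. Week 17 gives 7 × 16 + 1 = 113, as Table 3 states. Week 5 gives 29, and 29 + 26 = 55, the stated end of the Week 5 window. The same formula gives Week 9 = 57, Week 13 = 85, Week 25 = 169 and Week 33 = 225.

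**On-treatment windows as written.**

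| Time-point | Nominal day | Window | Day shared with next window |
|---|---|---|---|
| Week 5 | 29 | 2-55 | 55 |
| Week 9 | 57 | 55-83 | 83 |
| Week 13 | 85 | 83-111 | 111 |
| Week 17 | 113 | 111-167 | 167 |
| Week 25 | 169 | 167-223 | 223 |

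In general, shared days = upper limit − (spacing − 2) + 1. For 28-day spacing this is 26 − 26 + 1 = 1. For 56-day spacing it is 54 − 54 + 1 = 1. Through Week 105 there are 3 boundaries up to Week 17 and (105 − 17)/8 = 11 after it, so 14 shared days, the last being Day 727. Each is the later visit's nominal day minus 2, the earliest day that the ±2 tolerance permits.

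**When a shared-day form serves twice.** A Day 55 form is 26 days from Day 29 and 2 days from Day 57. If the Week 5 window holds a form closer to Day 29, that form is used for Week 5. If it does not, the Day 55 form satisfies the stated rule for both Week 5 and Week 9.

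**Follow-up 1.** The protocol permits 30 ± 7, or Days 23-37 after last dose. With the limits anchored at Day 30, the Table 3 window opens at 30 − 2 = Day 28 and closes at 30 + 68 = Day 98 or 30 + 82 = Day 112. The first clause of the same cell, read alone, takes any day up to 30 and so includes Days 23-27. The two readings disagree on those five days.

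**Follow-up 2.** The protocol permits 70 − 7 = 63 to 84 + 7 = 91 days after Follow-up 1, which is 29 days. Table 3 opens at 70 − 2 = 68 or 84 − 2 = 82. The permitted days before it opens are 63-67 (5 days) or 63-81 (19 days).

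Suppose Follow-up 1 took place on Day 30. A form 63-67 days later falls on Days 93-97, inside the Follow-up 1 window of 28-98. On the 84-day reading, a form 63-81 days later falls on Days 93-111, inside 28-112. Either way it is at least 63 days from Day 30, so the real Follow-up 1 form is closer and is kept. Follow-up 2 is then missing unless another form falls in its window. If Follow-up 1 was late, say Day 37, a form 63 days later is Day 100. On the 70-day reading that is after Day 98 and before Follow-up 2 opens at 37 + 68 = Day 105, so it lies in neither window.

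**Follow-up boundaries.** With Follow-up 1 on Day 30, the Follow-up 1/Follow-up 2 boundary depends on how the ranges pair:

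- +68 with 68, or +82 with 82: 1 shared day.
- +82 with 68: 15 shared days.
- +68 with 82: a 13-day gap.

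The 3-monthly window opens 5 days later than the protocol permits (91 − 2 = 89 against 91 − 7 = 84, assuming 3 months = 91 days). It shares 2, 1 or 0 days with the Follow-up 2 window if 3 months is 90, 91 or 92 days.

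**Check of the on-treatment correction.** Upper limits of Day 54, +25 and +53 give 2-54, 55-82, 83-110, 111-166, 167-222 and so on, with no gap and no overlap through Week 105.

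**The case against.** A reader might infer four stronger things. The documents do not support them.

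- *Every boundary overlaps by one day.* Baseline is "Prior to first dose on Day 1" and Week 5 starts on Day 2, so those two do not meet. The follow-up boundaries are not a fixed one day.
- *Forms on shared days are counted twice.* That happens only if the earlier window holds no closer form. Section 4.3.3.2 also speaks of assigning each form to a single time-point, which suggests that double use was not intended.
- *Valid questionnaires are discarded as missing.* The rule makes the time-point missing, not the form. An early Follow-up 1 form may fall in an on-treatment window, because those windows count from first dose and state no end at last dose.
- *A third of permitted Follow-up 1 days (5 of 15) are lost.* This needs the Day 30 anchor, and the first clause of the cell can be read otherwise. It would also be a share of calendar days, not of patients; the documents give no distribution of visit timing.

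Two further points stand in the plan's favour. Text just before Table 3 is redacted, and SAP Section 8 leaves further conventions to a Data Presentation Plan, so a resolving rule may exist elsewhere. And QoL is not among the visible primary or secondary endpoints.

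None of this removes the on-treatment overlap, which is plain arithmetic. The Follow-up 2 and 3-monthly mismatch does not depend on the Follow-up 1 wording.

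**Conclusion.** The point holds in a limited form. On treatment, 14 days through Week 105 each belong to two windows. Every one is a permitted visit day, and the visible text has no rule to settle it. In EQ-5D-3L follow-up, a Follow-up 2 form collected on 5 of the 29 permitted days (19 of 29 if 84 days is the anchor) comes before its window opens and can leave that time-point missing. The Follow-up 1 row is ambiguous rather than clearly late.

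This rests on three assumptions: nominal days follow the formula that reproduces Day 113 and Day 55, 3 months is about 91 days, and no overriding rule sits in redacted or separate text. How many patients would be affected cannot be estimated from the documents. The effect is limited to descriptive QoL summaries and completion rates; the primary safety endpoint is untouched.

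**What to change.** In SAP Table 3:

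1. Change Day 55 to Day 54, +26 to +25, and +54 to +53 in the Week 17 and 8-weekly rows.
2. Set the lower limits of the Follow-up 1, Follow-up 2 and 3-monthly windows to -7, to match protocol Table 5.1-3, and reword the Follow-up 1 row so that it has one reading.
3. Fix one nominal day for Follow-up 2 and state the date from which it counts. With -7, a nominal 70 opens at 63, the earliest permitted day. A nominal 84 would open at 77 and leave 63-76 outside, so it would need a wider lower limit.
4. End each preceding window the day before the next opens. If 3 months is set at 91 days, the +89 limits become +83, since the next window opens at 91 − 7 = 84.
5. End on-treatment windows where the Follow-up 1 window opens.

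Once the windows are disjoint, no rule for one form in two windows is needed. The cost is edits to one SAP table and the matching derivation code, with no change to data collection.

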Changes in tumor measurements and tumor responses to guide ongoing study treatment decisions should be assessed by the investigator using RECIST 1.1.

Per Amendment 08, the EQ-5D-3L and survival follow up will be collected for up to 2 years from the first dose of study therapy or until death, withdrawal of study consent, or lost-to-follow-up as indicated in the assessment table.

Statistical Considerations:

Sample Size: With an approximate 15% screening failure rate, a cohort of 735 screened PS1 patients is projected to a yield 640 treated patients. With $n = 640$ patients, about 3 will experience a rare adverse event with 0.5% true cumulative event rate with a rate estimated within 95% confidence interval (CI) (0.2%-1.1%). Approximately 2 patients with events and a 95% CI of (0%-1.1%) for assumed true event rate of 0.3% are projected.

Endpoints: The primary endpoint is the incidence for high-grade (CTCAE v4.0 Grade 3 or higher), treatment-related, select adverse events.

The secondary endpoints include:

- Incidence of all high-grade (Grades 3 and higher), select adverse events
- Median time to onset and median time to resolution (Grades 3-4) of select adverse events
- OS
- Investigator-assessed ORR

[REDACTED]

[REDACTED]

[REDACTED]

[REDACTED]

[REDACTED]

Analyses: The evidence for the research hypothesis of this clinical trial that high-grade (CTCAE v4.0 Grade 3 or higher), treatment-related select adverse events occur with a low frequency in patients with advanced (unresectable or metastatic) melanoma will be presented in terms of the number, percentage of subjects, and 95% confidence interval for the percentage with these select adverse events during treatment and off-treatment overall and by cohort.

Adverse events from date of enrollment up to last contact with patients will be presented for the full study duration and separately for events that occur on- or post-treatment. In particular, safety data will be summarized and listed for all treated patients using the NCI CTCAE version 4.0. All on-study AEs, drug-related AEs, SAEs, and drug-related SAEs will be tabulated using worst grade per NCI CTCAE v4.0 criteria by system organ class and MedDRA preferred term. On-study laboratory parameters including hematology, chemistry, liver function, thyroid function, and renal function will be summarized using worst grade per NCI CTCAE v4.0 criteria.

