8.4.6 Outcomes Research Analyses

The patients' self-report of their quality of life at baseline and change in their QoL in subsequent visits as recorded in the EORTC QLQ-C30 and EQ-5D-3L questionnaires will be summarized at each time point for the full safety analysis set. In addition, EORTC QLQ-C30 mean domain score and mean change from baseline in domain score will be reported. The overall global health score and domain score (functional and symptom score) for each patient will be calculated using the EORTC QLQ-C30 scoring algorithm. A mixed effects random model may be fitted for the mean change from baseline with time as the main factor and patient level characteristics like age, sex, Performance Status, and other patient characteristics as covariates.

Additionally, the EQ-5D-3L assessment will be performed. The EQ-5D-3L comprises 5 dimensions (mobility, self-care, usual activities, pain/discomfort and anxiety) and a visual analog rating scale). The responses to the EQ-5D-3L domains will be converted to health status index based on the European scoring algorithm.

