7.8.2 EuroQoL Five Dimensions Questionnaire

The following descriptive analyses will be conducted:

- EQ-5D-3L questionnaire completion rate, defined as the proportion of questionnaires actually received out of the expected number (i.e. number of subjects on treatment or in follow up), will be calculated and summarized for each assessment time point by treatment group.
- A by-subject listing of the level of problems in each dimension, corresponding to EQ-5D-3L health state (i.e., 5-digit vector), EQ-5D-3L utility index score, and EQ-5D-3L VAS score will be provided.
- Proportion of subjects reporting problems for the 5 EQ-5D-3L dimensions at each assessment time point will be summarized by level of problem and by treatment group. Percentages will be based on number of subjects assessed at assessment time point.
- For the EQ-5D-3L utility index and VAS scores, separately:
 - Mean score and mean change from baseline at each assessment time point will be summarized by treatment group using descriptive statistics (N, mean with SD and 95% CI, median, first and third quartiles, minimum, maximum).
 - A line graph summarizing the mean changes from baseline will be produced.

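### SAP Table 3 does not say which row takes an EQ-5D-3L form completed after the last dose; on its only workable reading the Week x means are on-treatment results, and no planned summary covers all treated patients by time since first dose

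*SAP*

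**What the plan says.** **Collection.** The protocol synopsis says that "the EQ-5D-3L and survival follow up will be collected for up to 2 years from the first dose of study therapy", unless the patient dies, withdraws consent or is lost first. Protocol Table 5.1-2 schedules the form every 4 weeks for 4 months and every 8 weeks after that while on treatment. Protocol Table 5.1-3 schedules it off treatment at FU-X01, at FU-X02 and then every 3 months. The QLQ-C30 has no row in Table 5.1-3, so the EQ-5D-3L is the only quality-of-life instrument that follows patients after they stop.

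**Windows.** In SAP Table 3 the Week rows are anchored on first dose. The Week 5 row is "Day 2 thru Day 55, inclusive". Weeks 9 and 13 run from 2 days before to 26 days after the nominal day. Week 17 and each 8-weekly row after it run from 2 days before to 54 days after. None of these rows is restricted to patients on treatment. Three EQ-5D-3L-only rows follow. Follow-up 1 applies "If assessment is post last dose and within 30 days of last dose", the next applies "If assessment is post 70-84 days of Follow-up 1 (+89 days/-2 days, inclusive", and the 3-monthly rows come after both.

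**Assignment and summary.** SAP 4.3.3.2 assigns each questionnaire to a time-point by these windows and treats a patient with no form in a window as missing there. SAP 7.8.2 states: "Mean score and mean change from baseline at each assessment time point will be summarized". Protocol 8.4.6 says that baseline quality of life and its change "will be summarized at each time point for the full safety analysis set".

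**The concern.** Table 3 uses two clocks, and a form completed after the last dose fits a row on each. If such forms go to the follow-up rows, a patient who stops at month 3 and completes a form at month 6 adds nothing to the month-6 mean and is counted as missing there.

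Patients stop early mainly for reasons tied to health status. Protocol 3.5 lists adverse events, intercurrent illness and progression without clinical benefit. The Week x curve would then describe patients still receiving nivolumab, and could appear to hold or rise as sicker patients leave it. The follow-up rows cannot fill the gap. Follow-up 1 pools forms from about 1 month after first dose, for a patient who had one dose, to about 2 years, for one who stopped near the end. A reader who wants EQ-5D-3L at one year for the treated population would find no table that gives it, although the forms exist.

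**Working it through.** **1. Reproduce Table 3.** Nominal day = (week − 1) × 7 + 1. Week 17 gives 16 × 7 + 1 = Day 113, as printed. Week 5 gives Day 29, and 29 + 26 = Day 55, as printed.

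**2. Coverage of the Week rows.** The windows are Week 5: Days 2–55; Week 9: 55–83; Week 13: 83–111; Week 17: 111–167; Week 25: 167–223; and so on to Week 97: 671–727 and Week 105: 727–783. No day from 2 to 731 is uncovered. If the Week rows took precedence, no follow-up row could receive a form within 2 years. With one time-point per form, the follow-up rows have content only if post-dose forms go there.

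**3. One patient, last dose at Week 9 (Day 57).** Off-treatment forms fall 30 days after last dose, 70 days after that (the early end of 70–84), and then every 91 days.

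| Form day | Week row containing that day |
|---|---|
| 87 | 13 |
| 157 | 17 |
| 248 | 33 |
| 339 | 49 |
| 430 | 57 |
| 521 | 73 |
| 612 | 81 |
| 703 | 97 |

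Counted from first dose, the 8 forms would fill 8 of the 12 Week rows from Week 13 to Week 97. On the step 2 reading they fill none. Weeks 25, 41, 65 and 89 would be empty either way, because off-treatment forms come only every 3 months.

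**4. Illustrative size at Week 49.**
- t = 336 / 30.4375 = 11.04 months (SAP 8.2 conversion).
- Survival is taken as exponential with median 16.8 months, the earlier nivolumab melanoma figure in Protocol 1.4.1. Alive = 0.5^(11.04/16.8) = 0.634.
- Median time on drug T is not in the documents. It is assumed to be 4 to 12 months, exponential. On drug = 0.5^(11.04/T).
- Share of survivors off drug = 1 − on drug / alive.
- The off-drug deficit is not in the documents. It is assumed to be 5 to 10 VAS points.
- Excess of the on-treatment mean over the mean of all survivors = share × deficit. This supposes that every off-drug survivor has a usable form.

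| T (months) | On drug | Share off drug | Excess (VAS points) | As % of the 7-point minimally important difference (SAP 4.3.3.2) |
|---|---|---|---|---|
| 12 | 0.529 | 0.167 | 0.8–1.7 | 12–24% |
| 8 | 0.384 | 0.394 | 2.0–3.9 | 28–56% |
| 6 | 0.279 | 0.559 | 2.8–5.6 | 40–80% |
| 4 | 0.148 | 0.767 | 3.8–7.7 | 55–110% |

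For the utility index, an assumed deficit of 0.08 (the SAP's minimally important difference) gives 0.167 × 0.08 = 0.013 to 0.767 × 0.08 = 0.061.

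**The case against.** Four arguments go the other way.

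- **The exclusion is not written down.** A reader might infer that the SAP expressly bars post-dose forms from the Week rows. It does not. Those rows carry no on-treatment condition and Table 3 has no precedence rule. Text just before Table 3 and at the head of SAP 7.8 is redacted, so a rule there cannot be ruled out. This stands: the exclusion is an inference, though the only one that gives the follow-up rows content.
- **The forms are not thrown away.** A reader might infer that data after stopping are lost. They are not. Follow-up 1, Follow-up 2 and the 3-monthly visits are assessment time points, and SAP 7.8.2 summarizes scores and changes at each. Decline after stopping would be visible there. This also stands. What those rows cannot give is a result at a fixed time since first dose.
- **No protocol commitment is broken.** Protocol 8.4.6 speaks of each time point and does not require time since first dose. Table 3 follows the protocol's own visit schedule, and separate on- and post-treatment reporting matches Protocol 8.4.2.2. This stands, and it is why the existing tables should be kept.
- **The size is assumed.** Time on drug and the off-drug deficit appear nowhere in the documents. The survival median comes from 107 patients pooled over doses of 0.1 to 10 mg/kg. A reader might take any one row of the table above as the bias. The range of 12% to 110% of the minimally important difference shows that the size is not known, and the direction is likely but assumed.

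One possible answer does not meet the point. SAP 8.4 mentions mixed and pattern-mixture models, but does not say that post-dose forms enter them on a first-dose time scale.

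**Conclusion.** The point holds in a limited form. Table 3 needs a precedence rule. On its only workable reading, the Week x means and line graph are on-treatment results, and no planned EQ-5D-3L summary combines on- and off-treatment forms by time since first dose. The conclusion rests on the follow-up row definitions together with one time-point per form. It also takes the protocol's 2-year collection limit; SAP 2.1 still says 5 years.

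Read as the health of the treated population, the curve is probably too favourable. The illustration at Week 49 is 0.8 to 7.7 VAS points, with time on drug and the off-drug deficit both assumed. The documents do not support a narrower figure, or a claim that data are discarded. EQ-5D-3L is not listed among the primary or secondary endpoints and no test or decision depends on it, so severity is low.

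**What to change.** 1. In SAP Table 3, state that forms completed after the last dose go to the follow-up rows. Label the Week x tables and line graph in SAP 7.8.2 as on treatment. Keep them and the follow-up tables.
2. Add to SAP 7.8.2 a summary of the utility index, VAS and five dimensions, with a line graph, that assigns every EQ-5D-3L form by days since first dose, on or off treatment, through month 24. Use windows that do not overlap; the present Week windows share their boundary days. State that each mean describes patients alive with a form.
3. Match the completion-rate denominator to each display. SAP 7.8.2 counts patients on treatment or in follow-up, which at a Week x row could include patients whose forms are filed elsewhere.

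**Cost.** SAP wording and one more derivation, with no new data. No window width suits both schedules. The existing 8-week rows leave some windows without an off-treatment form (4 of 12 in the example). Windows 12 weeks apart, centred on Weeks 25, 37, 49 and so on to 97, would put Weeks 33 and 41, 57 and 65, and 81 and 89 in shared windows. With one form used per window, 3 of the 10 scheduled on-treatment forms from Week 25 to Week 97 would be unused. That is acceptable in an added display, and is a reason not to replace the current one.
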